9. STUDY CALENDAR

Baseline evaluations are to be conducted within 3 weeks prior to start of protocol therapy (except for pregnancy test and baseline tumor biopsy, as detailed). If these screening assessments occur within 3 days before start of study treatment, then they may serve as the baseline cycle 1 day 1 values. Each treatment cycle will be 14 days long. Subjects may be dosed no less than 12 days between doses.

As detailed in the Study Calendar, a negative pregnancy test in women of child-bearing potential must be documented within 24 hours before the first dose of study medication.

Correlative tissue collection obtained before starting protocol therapy, should be performed if archival tissue is not available.

In the event that the participant's condition is deteriorating, laboratory evaluations should be repeated within 48 hours prior to initiation of the next cycle of therapy.

Assessments must be performed prior to administration of any study agent. Study assessments and agents should be administered within ± 3 days of the protocol-specified date, unless otherwise noted.

Scans must be done ≤ 4 weeks prior to the registration.

CONFIDENTIAL

This document is confidential. Do not disclose or use except as authorized.

	Screening	Week 1	Week 3	Presurgery/surgery (week 3-4)	Week 10-20	3 months after all treatment	3 months to 1 year ^l	1 year visit ^l	Survival follow up by phone ^m
Informed consent	X								
Medical History	X								
Physical exam (Ht, Wt, VS, PS) ^a	X	X	X			X ⁱ	X ⁱ	X ⁱ	
B-HCG ^b	X								
Routine labs ^d	X	X ^c	X	X					Xi
Screening labs/ECG ^e	X								
Adverse event evaluation ^f	X	X	X			X ⁱ	X ⁱ		
Radiologic evaluation ^g	X			X					
Correlative blood collection ^h	X			X	X		X		X
Correlative tissue collection	X ^j			X ^k					
Study Agent - Nivolumab		X	X						
Study Agent - Ipilimumab(cohort 2 only)		X							

a. Height is taken only at screening.
 
b. Serum or urine pregnancy test (women of childbearing potential), within 24 hours of the first dose of nivolumab.
 
c. Not needed if pre-study labs performed within 3 days of Day 1.
 
d. CBC with differential, comprehensive chemistry panel including LDH, AST, ALT, ALP, T.Bili, BUN or serum urea, Cre, Ca, Mg, Na, K, Cl, Glucose, amylase, lipase, phosphorus, albumin, and total protein as well as TSH, Free T4, and Free T3.
 
e. Routine labs as per D, and also HBVsAg, HCV Ab or HCV RNA. EKG is required only at screening and as clinically indicated. If patient is not high risk, negative tests results don't need to be result for study enrollment.
 
f. In addition to specified time points, adverse effects will also be continuously monitored.
									

CONFIDENTIAL

This document is confidential. Do not disclose or use except as authorized.

g. Imaging will include CT neck/chest and/or PET-CT. MRI neck may be performed instead of CT neck.h. Correlative blood collections will be timed to coincide with blood drawn for other reasons, but will in general be scheduled at baseline, week 3-4 and then after surgery and before adjuvant treatment (week 10-20), if indicated. Additional optional research blood draws may be taken during routine follow up to year 3.i. Not performed if patient receiving care at outside institution. All efforts will be made to obtain outside medical records.j. Archival tissue may be used.k. Obtained at the time of surgery (week 3-4).l. Visits will occur approximately every 2-3 months over the first year. Medical records from local evaluations may be provided if patient is unable to follow up at study site.m. 1 year after enrollment (+/-2 weeks), patients will be restaged with a clinical exam, CT neck/chest and/or PET-CT as per standard of care. This is optional, but highly encouraged. Medical records from local evaluations may be provided if patient is unable to follow up at study site.n. After the 1 year visit, follow up for survival will continue by phone. Patients will be contacted by phone, every 3 +/- 1 month, for up to 3 years from enrollment.	
--	--

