6. DOSING DELAYS/DOSE MODIFICATIONS

Toxicity assessments will be done using the CTEP Active Version of the NCI Common Terminology Criteria for Adverse Events (CTCAE **version 4.0**) which is identified and located on the CTEP website at: http://evs.nci.nih.gov/ftp1/CTCAE/CTCAE_4.03_2010-06-14_QuickReference_8.5x11.pdf

If possible, symptoms should be managed symptomatically. In the case of toxicity, appropriate medical treatment should be used (including anti-emetics, anti-diarrheals, etc.).

All adverse events experienced by participants will be collected from the time of the first dose of study treatment, through the study and until the final study visit 1 year after enrollment. Participants continuing to experience toxicity at the last scheduled study visit may be kept on the study until the toxicity has resolved or is deemed irreversible.

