6.1 Anticipated Toxicities

Adverse events (both non-serious and serious) associated with nivolumab with or without ipilimumab exposure may represent an immunologic etiology. These adverse events may occur shortly after the first dose or several months after the last dose of treatment. Most related AEs are thought to be due to the effects of inflammatory cells on specific tissues. Please refer to Appendix D and E and the current versions of Investigator's Brochures for expected toxicities related to nivolumab and ipilimumab.

As there is potential for hepatic toxicity with nivolumab or nivolumab/ipilimumab combinations, drugs with a predisposition to hepatotoxicity should be used with caution in patients treated with nivolumab-containing regimen.

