All patients who initiate protocol therapy will also be evaluated for response using RECIST v1.1, pathologic response at the time of surgery, safety and tolerability, local failure rate, regional failure rate, local and regional progression free-survival and overall survival. PFS and OS will be analyzed using Kaplan–Meier product-limit estimates and will be plotted using Kaplan-Meier plots. PFS is defined as the time from study randomization to disease progression according RECIST 1.1, medical judgment or death due to any cause, whichever occurred first. Patients alive without disease progression are censored at the date of last disease evaluation. The hazard ratio for each time-to-event endpoint will be estimated with 95% confidence intervals derived from the Cox proportional hazard model, but no hypothesis testing will be conducted. Other definitions are provided in section 10.1.

All patients will be evaluable for toxicity from the time of their first treatment with any study agent. Toxicity will be graded according to NCI CTCAE, Version 4.0. Toxicities will be summarized by maximum grade and by treatment arm. Incidence rate of each toxicity will be reported with 95% exact CI.

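### Late adverse-event evaluations are not performed for patients treated elsewhere, yet all treated patients stay in the toxicity denominator, so late toxicity rates can be understated by an unknown amount.

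*Combined protocol and SAP*

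**What the plan says.** **Collection period.** Section 6 has all adverse events collected from first dose "until the final study visit 1 year after enrollment". Section 6.1 warns that drug-related events may begin "several months after the last dose of treatment". Section 11.8 refers to events up to 30 days after the last study intervention, taken as the cycle 2 dose, and asks that these be followed to resolution. The serious-event reporting in Sections 11.4 and 11.7 uses the same 30 days.

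**Calendar (Section 9).** The row "Adverse event evaluation" is marked at screening, week 1 and week 3, and then at two late points: 3 months after all treatment, and 3 months to 1 year. Both late marks carry footnote i: "Not performed if patient receiving care at outside institution". The footnote continues: "All efforts will be made to obtain outside medical records". As extracted, the row is blank at surgery, at week 10-20 and at the 1-year visit, although a physical exam is marked at 1 year. Footnote f on the row adds: "In addition to specified time points, adverse effects will also be continuously monitored". Footnote l, on follow-up visits in the first year, allows: "Medical records from local evaluations may be provided if patient is unable to follow up at study site".

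**Analysis (Section 14).** All patients are evaluable for toxicity from first treatment, and "Incidence rate of each toxicity will be reported with 95% exact CI". Nothing is said about patients whose late adverse-event follow-up is incomplete.

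**The concern.** Section 6 sets a one-year collection period, but the calendar does not schedule the evaluations that would fill it for everyone. For a patient who has adjuvant therapy or follow-up elsewhere, week 3 is the last marked adverse-event evaluation. After that, ascertainment depends on what an outside clinic charted and what the study team could obtain.

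Section 14 then divides by all treated patients. A late event that nobody records cannot enter the numerator, while the patient remains in the denominator. The error can therefore only push the rate down, and the exact interval is computed as though all 20 patients in the arm had been fully observed.

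The late part of the safety profile is at stake. These patients have resectable disease and curative-intent surgery, so delayed immune toxicity is a relevant cost of a short window treatment. Section 15 also allows extra time before publication for toxicity, so late events are meant to be reported.

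**Working it through.** **Step 1. Passages side by side.**

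| Topic | Section 6 / 6.1 | Section 9 calendar | Section 11.8 |
|---|---|---|---|
| End of adverse-event period | 1-year visit | Last mark at 3 months to 1 year; none at the 1-year visit | 30 days after cycle 2 dose |
| Patients followed elsewhere | No exception | Late evaluations dropped, records sought | No exception |

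Section 5.4 also promises close monitoring of toxicity after surgery and during adjuvant treatment, but no adverse-event mark appears at surgery or week 10-20. Section 11.2 has events assessed at every evaluation time point. That would cover the 1-year exam if it takes place, but footnote i is attached to that exam too.

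**Step 2. Inputs for the size.** The 20 patients per arm come from Section 14. The documents give no late-event rate, no share followed outside and no recovery rate from outside records. There is no plan figure to reproduce, and the following are assumptions:
- true late-event rate p = 20%;
- number followed outside per arm, k = 4, 8 or 12;
- share of their late events recovered from records, c = 0, 0.5 or 1.

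**Step 3. Expected observed rate** = p × [(20 − k) + c × k] / 20.

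| k | c = 0 | c = 0.5 | c = 1 |
|---|---|---|---|
| 4 | 0.20 × 16/20 = 16% | 0.20 × 18/20 = 18% | 20% |
| 8 | 0.20 × 12/20 = 12% | 0.20 × 16/20 = 16% | 20% |
| 12 | 0.20 × 8/20 = 8% | 0.20 × 14/20 = 14% | 20% |

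At half recovery the shortfall is 2 to 6 percentage points. For scale, the exact 95% interval for 4/20 is 5.7% to 43.7%.

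**Step 4. Limiting case for the interval.** With zero events among n patients, the two-sided exact 95% upper limit is 1 − 0.025^(1/n). For 0/20 this is 16.8%. If outside records carried no information at all (c = 0), the patients actually observed would give 20.6% (0/16), 26.5% (0/12) or 36.9% (0/8). These figures belong to the c = 0 column only and should not be combined with half recovery. Section 14 does not plan a separate late-event rate, so they illustrate the loss of information and are not a planned output.

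**The case against.** The strongest reply is that footnote i replaces a visit with record retrieval, and that other routes exist. Footnote f provides for continuous monitoring, footnote l accepts local records, and Section 11.2 records events found by any means. Section 11.8 asks participants to report serious, possibly related late events and investigators to notify the overall principal investigator. This stands in part: adverse-event collection is not abolished for these patients. However, none of these routes requires a contact at a set time, grading of what is found, or complete abstraction. Footnote l is permissive, and the Section 11.8 request to participants covers serious events only.

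Four stronger readings may tempt a reader, and the documents do not support them.
- *Unevaluated patients are counted as event-free.* No section says so. These patients still contribute window-period events and anything found in records. The supported statement is that late events not captured lower the rate.
- *The primary safety endpoint is biased.* Section 14 defines that endpoint by dose-limiting toxicities, and Section 5.4 ends their window at surgery, before footnote i applies.
- *The bias differs between arms.* Nothing shows this. Once both run-ins are complete, assignment is randomized, and no toxicity comparison is planned.
- *Sections 6 and 11.8 flatly contradict each other.* Section 11.8 may govern only which events are followed to resolution. Its heading, which refers to the observation period, leaves this open, so the two sections need reconciling.

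The calendar was machine-read and shows signs of shifted cells: a routine-lab mark sits under telephone follow-up, and the column footnote letters do not match the notes. The blank 1-year cell must therefore be checked in the source PDF. The footnote i point does not depend on that cell.

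**Conclusion.** The concern holds for the descriptive late-toxicity rates. Followed as written, the plan can understate them, because scheduled late ascertainment is withdrawn for an unspecified group who remain in the denominator. The direction is downward whenever any outside event is missed. The size cannot be determined from the documents: it ranges from nothing, with full recovery, to the 18% to 14% expected rates at half recovery, against an assumed true 20%. Those shifts are small beside the sampling error of one arm. Unlike sampling error, though, they are not reflected in the reported interval. Neither the dose-limiting toxicity rule nor the response decision is affected. This is worth correcting because the correction is cheap and late events are an intended output, but it does not invalidate the safety assessment of the window period.

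**What to change.** 1. State one adverse-event collection period and use it in Sections 6, 9 and 11.8. If Section 11.8 is meant only to define which events are followed to resolution, say so.
2. For the adverse-event row, replace the not-performed rule in footnote i with a telephone adverse-event evaluation at the same time points, graded by CTCAE and supplemented by required abstraction of outside records into the case report form.
3. Mark an adverse-event evaluation at the 1-year visit to match Section 6, after checking that cell in the source PDF.
4. In Section 14, keep the all-treated rate. Add, by arm, the number with adverse-event ascertainment through each late time point, and a cumulative incidence of late events that censors at the last adverse-event assessment. State its assumption that stopping assessment is unrelated to toxicity risk.

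Restricting the denominator to patients with at least one post-surgery evaluation is not a good substitute. It drops patients who die or leave first, and it treats one early contact as a full year of observation.

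The cost is a few short calls per outside patient in year 1 (footnote n already plans telephone contact from year 1 to year 3), a calendar edit and a short addition to Section 14. The late-toxicity intervals will be somewhat wider.

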10. MEASUREMENT OF EFFECT

The main focus of this trial is to determine safety and response in the window period where the two investigational agents will be investigated. Thus patients will be examined and staged as part of the screening process and then again following window treatment prior to surgery. Pathologic evaluation will also be performed at the time of surgery. Following surgery (and adjuvant therapy, if indicated), follow up will be as per standard of care, with an emphasis on monitoring of disease-free and overall survival.

10.1 Antitumor Effect– Solid Tumors

For the purposes of this study, participants should be re-evaluated for response at week 3-4 following window treatment and prior to definitive surgery.

There is currently some uncertainty about how best to monitor response to immunotherapy [47], as well as how best to monitor response in the preoperative window setting [48, 49]. Additionally, assessing radiologic response in the oral cavity can be complicated by dental artifact and head position. Therefore, response will be assessed in multiple ways using clinical, radiologic and pathologic data. Thus, although our primary endpoint will utilize volumetric measurements (obtained either radiologically, clinically or pathologically) that have been previously investigated in this setting [48], international RECIST criteria will also be measured as a secondary endpoint. Changes in the diameter (unidimensional axial measurement) of the tumor lesions are used in the RECIST criteria. We will also evaluate pathologic response defined below.

10.1.1 Definitions

Evaluable for toxicity. All participants who receive at least one dose of study treatment will be evaluable for toxicity from the time of their first treatment.

Evaluable for objective response. Only those participants who have measurable disease present at baseline (either by clinical exam or imaging), have received at least one cycle of therapy, and have had their disease re-evaluated will be considered evaluable for response. These participants will have their response classified according to the definitions stated below. (Note: Participants who exhibit objective disease progression or die prior to the end of treatment will also be considered evaluable.)

10.1.2 Disease Parameters

Measurable disease. Measurable disease is the presence of at least one lesion that can be accurately measured in at least one dimension with longest diameter ≥ 20 millimeters (mm) using conventional techniques (CT, MRI, x-ray, PET-CT or clinical exam) or ≥ 10 mm with spiral CT scan. Measurable lesions must be at least 2 times the slice thickness in mm. All tumor measurements must be recorded in millimeters (or decimal fractions of centimeters). In the oral cavity, imaging modalities may be obscured by dental artifact, or normal mucosa; therefore, clinical exam or pathologic measurements may suffice.

Non-measurable disease. All other lesions (or sites of disease), including small lesions (longest diameter <20 mm with conventional techniques or <10 mm using spiral CT scan), are considered non-measurable disease.

Target lesions. All measurable lesions up to a maximum of 10 lesions in total, should be identified as target lesions and recorded and measured at baseline. Target lesions should be selected on the basis of their size (lesions with the longest diameter) and their suitability for accurate repeated measurements (either by imaging techniques or clinically). A sum of the longest diameter (LD) for all target lesions will be calculated and reported as the baseline sum LD. The baseline sum LD will be used as the reference by which to characterize the RECIST objective tumor response. Volumetric measurements may also be made using imaging software using contouring software or by obtaining measurements in at least 2 dimensions or by multidimensional measurements obtained from clinical exam.

Non-target lesions. All other lesions (or sites of disease) including any measurable lesions over and above the 10 target lesions should be identified as non-target lesions and should also be recorded at baseline. Measurements of these lesions are not required, but the presence or absence of each should be noted at each follow-up.

10.1.3 Methods for Evaluation of Measurable Disease

All measurements should be taken and recorded in metric notation, using a ruler, calipers, or digital measurement tool. All baseline evaluations should be performed as closely as possible to the beginning of treatment and never more than 4 weeks before the beginning of the treatment.

The same method of assessment and the same technique should be used to characterize each identified and reported lesion at baseline and during follow-up. Imaging-based evaluation is preferred to evaluation by clinical examination when both methods have been used to assess the anti-tumor effect of a treatment.

Clinical lesions. Clinical lesions will only be considered measurable when they are superficial or mucosal (e.g., skin nodules, oral cavity primaries and palpable lymph nodes). In these cases, documentation by color photography, including a ruler to estimate the size of the lesion, is recommended.

Conventional CT and MRI. These techniques should be performed with cuts of 10 mm or less in slice thickness contiguously.

10.1.4 FDG PET and PET/CT. The acquisition of FDG PET and FDG PET/CT scans should follow the NCI Guidelines for using FDG PET as an indicator of therapeutic response (L.K. Shankar, J.M. Hoffman, S. Bacharach, M.M., et al. Consensus recommendations for the use of 18F-FDG PET as an indicator of therapeutic response in patients in National Cancer Institute Trials. J Nucl Med, 47(6):901-903, 2006 or <http://www.ncbi.nlm.nih.gov/pubmed/16741317>). Patients should avoid strenuous exercise and be on a low carbohydrate diet for 24 hours prior to the scan. Patients should fast for 4 hours or longer prior to the FDG injection and should have a serum glucose

of less than 200 mg/dL at the time of FDG injection. A 10-20 mCi dose of FDG should be injected for typical adult patients.

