1.2 Primary Objectives

- To determine the 1) safety, tolerability; and 2) response rate to window treatment with single agent nivolumab or nivolumab combined with ipilimumab using bidirectional measurements (product of longest 2 diameters of lesions) of primary and nodal lesions to be removed at the time of surgery

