3. PARTICIPANT SELECTION

3.1 Eligibility Criteria

Participants must meet the following criteria on screening examination to be eligible to participate in the study:

1. Pathologically confirmed squamous cell carcinoma of the oral cavity. Clinical stage \geq T2 (primary tumor greater than 2 cm in size) and/or evidence of regional nodal involvement by clinical exam or imaging
2. Only patients 18 years and older are eligible. There is no upper age limit but the patients must be able to medically tolerate the regimen. Adverse event data are currently unavailable on the use immune checkpoint blockade for participants < 18 years of age, and thus children are excluded from this study
3. ECOG performance status \leq 1 (see Appendix A)
4. Patients must be a surgical candidate (e.g. their disease must be considered resectable before any treatment and must have no serious medical contraindications that definitively preclude undergoing general anesthesia)
Ability to understand and the willingness to sign a written informed consent document
5. Women of childbearing potential (WOCBP) must agree to use appropriate method(s) of contraception (see Appendix B). WOCBP should use an adequate method to avoid pregnancy for 23 weeks (30 days plus the time required for nivolumab to undergo five half-lives) after the last dose of investigational drug. WOCBP is defined as any woman or adolescent who has begun menstruation and is not post-menopausal. A post-menopausal woman is defined as a woman who is over the age of 45 and has not had a menstrual period for at least 12 months

CONFIDENTIAL

This document is confidential. Do not disclose or use except as authorized.

6. Women of childbearing potential must have a negative serum or urine pregnancy test (minimum sensitivity 25 IU/L or equivalent units of HCG) to be scheduled within 24 hours prior to the start of nivolumab
7. Men who are sexually active with WOCBP must agree to use any contraceptive method (see Appendix B) with a failure rate of less than 1% per year. Men receiving nivolumab and who are sexually active with WOCBP will be instructed to adhere to contraception for a period of 31 weeks after the last dose of investigational product. Women who are not of childbearing potential (ie, who are postmenopausal or surgically sterile as well as azoospermic men do not require contraception)
8. Participants must have normal organ and marrow function as defined below:

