10.1.5 Response Criteria

10.1.5.1 Evaluation of Target Lesions

Volumetric Analysis

As previously described [48], volumetric response will be determined by measuring measurable and non measurable primary and nodal disease in at least two dimensions as determined by scan, clinical exam or pathology. If measurement in two dimensions is not possible due to irregular shape of the lesion, comparison of the single largest dimension measured may be used. In all cases, serial photographs are strongly recommended to help assess response. Responders will have demonstrated any decrease in overall tumor volume. Primary and nodal volume will also be assessed separately in terms of response.

RECIST Criteria

Complete Response (CR): Disappearance of all target lesions.

Partial Response (PR): At least a 30% decrease in the sum of the longest diameter (LD) of target lesions, taking as reference the baseline sum LD.

Progressive Disease (PD): At least a 20% increase in the sum of the longest diameter (LD) of target lesions, taking as reference the smallest sum LD recorded since the treatment started or the appearance of one or more new lesions (new lesions must be > slice thickness).

Stable Disease (SD): Neither sufficient shrinkage to qualify for PR nor sufficient increase to qualify for PD, taking as reference the smallest sum LD since the treatment started.

Unknown (UN): Assessment of target lesions cannot be made due to insufficient or unevaluable data. In this case, a concise explanation must be given.

Note: If tumor response data is missing for target lesions, the overall assessment must be UN unless there is new disease that would result in an overall assessment of PD. However, if there is missing or unevaluable data for non-target lesions, but data is available for all target lesions, the overall response for that time point will be assigned based on the sum LD of all target lesions. Additionally, the assessment of CR cannot be made if there is missing or unevaluable data for non-target lesions. In this case, the overall assessment would be PR.

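### Section 10.1.3 allows CT/MRI slices up to 10 mm for a co-primary endpoint that counts any decrease as response, so in lesions near 2 cm slice position alone can misclassify small true changes; a lower, matched ceiling would largely remove this.

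*Combined protocol and SAP*

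**What the plan says.** Section 10.1.3 gives the only absolute limit on slice thickness, for conventional CT and MRI: "These techniques should be performed with cuts of 10 mm or less in slice thickness contiguously". It asks for the same method and technique at baseline and follow-up, and adds that "Imaging-based evaluation is preferred to evaluation by clinical examination when both methods have been used".

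Section 10.1.2 adds a relative limit: "Measurable lesions must be at least 2 times the slice thickness in mm".

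The volumetric endpoint is defined in section 10.1.5.1: "Responders will have demonstrated any decrease in overall tumor volume". Primary and nodal disease, both measurable and non-measurable, is to be measured "in at least two dimensions as determined by scan, clinical exam or pathology". Section 1.2 words the same objective as "bidirectional measurements (product of longest 2 diameters of lesions", and section 10.1.2 also allows contouring software.

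Section 3.1 admits patients at clinical stage T2 or above ("primary tumor greater than 2 cm in size"), with regional nodal involvement as an alternative route. Section 10.1.10 rules out central review. Section 14 uses the response count in two rules per arm: promising if at least 6 of 20 respond, and stop enrolment if none of the first 10 respond.

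**The concern.** With 10 mm slices a 20 mm tumour appears on two or three images. Which cross-sections those images show depends on where the slice stack falls, and that can differ between the baseline scan and the scan at week 3 or 4. Section 10.1 itself names head position as a difficulty in the oral cavity. Measured size can therefore change while the tumour does not.

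An endpoint with a response margin would absorb some of this. Here the margin is zero, so any shift larger than the true change, and opposite to it, reverses the patient's status. At stake is the responder count behind the 6-of-20 and 0-of-10 rules.

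**Working it through.** **The plan's own figure.** The one-sided 90% exact lower bound is 16.6% for 6/20 and 12.7% for 5/20, so 6 is the right cut-off for a 15% bound. At a true rate of 15%, P(6 or more of 20) = 0.067. The documents give no measurement-error figure to reproduce.

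**Inputs from the plan.** Slice thickness T = 10 mm (ceiling, 10.1.3); lesion diameter 20 mm (lower edge of the T2 criterion, 3.1); metric either the diameter product (1.2) or contoured volume (10.1.2); response threshold zero (10.1.5.1).

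**Assumptions of mine.** The lesion is a sphere of radius R. Each slice shows the cross-section at its mid-plane. Slice position is random and independent on the two scans.

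**Step 1, diameter product.** If the nearest slice centre lies c from the equator (0 to T/2), the largest visible diameter is 2√(R² − c²). The worst-case loss of product is therefore (T/2)²/R².
- 20 mm lesion, c = 5 mm: diameter 2√75 = 17.3 mm, product 300 against 400 mm², a fall of 25% (a rise of 33% in reverse).
- 30 mm lesion: 25/225 = 11%. 40 mm lesion: 25/400 = 6%. 15 mm node: 25/56.25 = 44%.
- 20 mm lesion on 5 mm slices: 6.25/100 = 6%. On 3 mm slices: 2.25/100 = 2%.

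**Step 2, slice-summed volume.** V = T × Σπ(R² − z²), against a true volume of (4/3)πR³ = 1333π mm³.
- Slice centres at ±5 mm: 10 × 2 × 75π = 1500π (1.125 of truth).
- Slice centres at 0 and ±10 mm: 10 × 100π = 1000π (0.75 of truth).
- The largest fall between scans is 500/1500 = 33%.

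The position giving the largest product gives the smallest volume, so the two permitted metrics can disagree on the same pair of scans.

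**Step 3, typical size.** With random positions at 10 mm slices, the product of an unchanged 20 mm lesion changes by a median of 7.6%. The 95th percentile is 23.6%, and P(change of 20% or more) = 0.11. If each slice averages over its thickness with a 50% edge threshold, the worst case is a 20% fall or a 25% rise. A single diameter, under the mid-plane model, moves by 13% down or 15% up at worst.

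**Step 4, misclassification.** A 10% volume increase multiplies the diameter by 1.1^(1/3) = 1.032; a 10% product increase multiplies it by 1.1^(1/2) = 1.049. The entries give the share of simulated scan pairs in which true growth reads as a decrease; true shrinkage of 10% is missed at nearly the same rates.

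| Lesion and true change | 10 mm | 5 mm | 3 mm |
|---|---|---|---|
| 20 mm, 10% in volume (either metric) | 26% | 0% | 0% |
| 20 mm, 10% in product (read by product) | 18% | 0% | 0% |
| 15 mm node, 10% in volume (read by product) | 34% | 10% | 0% |
| 30 mm, 10% in volume | about 9% | 0% | 0% |
| 40 mm, 10% in volume | 0% | 0% | 0% |

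**Step 5, effect on the rule (boundary case only).** If all 20 patients in an arm had 20 mm lesions that grew 10% in volume and were read on 10 mm slices, then P(6 or more of 20 at p = 0.26) = 0.42. At 5 mm or 3 mm it would be about 0.

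**Step 6, no true change.** With sizes on a continuous scale, P(measured decrease) = 0.50 at every thickness, and P(6 or more of 20 at p = 0.50) = 0.979. Rounding diameters to whole millimetres lowers the 0.50 to 0.33 at 10 mm, 0.10 at 5 mm and 0 at 3 mm, but only if slice position is the sole source of error.

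**The case against.** The strongest reply is that 10 mm is a ceiling, not a practice. The documents nowhere say what thickness sites use. Section 10.1.2 treats 10 mm lesions as measurable on spiral CT, and its two-times rule then implies slices of 5 mm or less for those lesions. A 2 cm lesion is also the bottom edge of one eligibility route, and the effect fades with size. All of this stands, and it limits how often the problem would arise.

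A reader might infer that slice position routinely moves a 2 cm tumour's size by 25–33%. The documents do not support that. The two figures belong to different metrics, and each needs a sphere, slices at the ceiling and opposite extreme positions on the two scans. Nor do they support the view that only 3 mm will do: in this model 5 mm already removes the error for a 20 mm lesion at a 10% change, and 3 mm matters chiefly for small nodes.

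The safeguards in the plan help less than they seem to. Using the same technique does not fix slice position. The two-times rule does not bound this endpoint, because 10.1.5.1 also counts non-measurable disease. Clinical exam and pathology are permitted sources, but 10.1.3 prefers imaging to clinical exam. Response is judged on overall tumour volume, so a single node's 44% worst case is diluted when summed with the primary.

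The last objection is that the zero threshold is the deeper fault, and thin slices do not cure it. That is correct. The two problems are separate and so are their remedies.

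**Conclusion.** The point holds as a limited weakness. At the permitted ceiling, and for lesions near 20 mm, slice position can reverse the response status of a patient with a small true change: about 26% of scan pairs at 10% in volume, or 18% at 10% in product, against 0% at 5 mm or 3 mm. The direction is secure. The size rests on a spherical shape, mid-slice reading and independent random positions, and on sites actually using slices near 10 mm, which the documents neither state nor exclude.

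One might go further and conclude that the trial's response count is unreliable for this reason. That does not follow: neither the thickness in use nor the lesion-size mix is given, and at 40 mm a 10% change is not misclassified at all. The change is still worth making, because it tightens a stated rule for a co-primary endpoint at little cost.

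**What to change.** In section 10.1.3, for neck CT or MRI used for the volumetric endpoint:
- Lower the ceiling to 5 mm, and to 3 mm or less where available, chiefly for small nodes.
- Require the same modality, slice thickness and plane at baseline and before surgery.
- Where a pair cannot meet this, record the fact. Use clinical bidirectional measurements instead only if they were taken at both time points and the lesion is superficial or mucosal. Otherwise keep the imaging pair and flag it for a sensitivity analysis.

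The fallback needs these conditions because sections 5.2.1 and 5.2.2 only encourage clinical measurements, deep nodes have none, and 10.1.3 prefers imaging. The new rule should be worded as an explicit exception to that preference.

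The cost is a short amendment with no added visit. The downside is that some outside baseline scans and some MRI scans will not meet the limit and will go to the fallback or the sensitivity analysis. A minimum decrease larger than measurement error would have to be set separately in section 10.1.5.1.
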